**Table 3: Patient Global Impression of Change (PGIC) Scale**

Since starting the study drug, how would you rate the change in your symptoms?	
Score	Description
1	Very much improved
2	Much improved
3	Minimally improved
4	No change
5	Minimally worse
6	Much worse
7	Very much worse

Note: Subjects will be considered improved if they have a PGIC of 1, 2, or 3 (very much improved, much improved, or minimally improved). Subjects with missing values will be considered not improved.

- Polyp grading of each nasal cavity, determined by a nasal polyp grading scale score measured by nasoendoscopy ([Table 4](#)) ([Lildholdt et al, 1995](#); [Lildholdt et al, 1997](#)). The baseline assessment of polyp grading is performed at Visit 1 (Screening) and Visit 6/Week 24/ET by the examining physician.

**Table 4: Nasal Polyp Grading Scale**

Score	Description
0	No polyps
1	Mild polyposis - polyps not reaching below the inferior border of the middle turbinate
2	Moderate polyposis - polyps reaching below the inferior border of the middle concha, but not the inferior border of the inferior turbinate
3	Severe polyposis - large polyps reaching below the lower inferior border of the inferior turbinate

### 7.3 Health Economic Assessments

Health economic information related to bilateral CRS will be collected during the study and will include information on criteria for surgical intervention (independent of actual surgery performed), subjects approved for surgery, who no longer elect to undergo surgery, and missed work or school days/lost productivity. The investigator will ask the subject if he/she would consider surgery and the subject will complete the HPQ (1-2 minutes to complete).

Objective criteria for surgical intervention are as follows:

- those with polyps present who have:
  - used a topical intranasal corticosteroid ( $\geq 8$  weeks duration)
  - used a short-course of systemic corticosteroid (1- to 3-week duration)

- SNOT-22 total score  $\geq 20$
- Lund-Mackay CT score  $\geq 1$
- those without polyps present who have:
  - used topical intranasal corticosteroid ( $\geq 8$  weeks duration)
  - used either a short course of broad-spectrum/culture-directed systemic antibiotic (2 to 3 weeks duration) or a prolonged course of systemic low-dose anti-inflammatory antibiotic (ie, macrolide or trimethoprim/sulfamethoxazole) ( $\geq 12$  weeks duration)
  - SNOT-22 total score  $\geq 20$
  - Lund-Mackay CT score  $\geq 1$
- subjects who enter the study approved for surgery with a scheduled surgery date, who no longer elect to undergo surgery
- The work productivity questionnaire asks about employment status, work absences, and on-the-job productivity. Subjects will also be asked to provide annual salary and postal code information at screening which will be used to inform overall cost to employers from lost work productivity.

## 7.4 Safety Assessments

Refer to the [Schedule of Study Procedures and Evaluations](#), for the timing of all safety assessments.

Safety will be assessed by performing a physical examination and evaluating clinical laboratory variables at Visit 1 (Screening), and throughout the study based on monitoring of AEs (as described in [Section 8](#)), performing nasal examination, measuring vital signs (ie, blood pressure, pulse) and weight, and through collection of information for concomitant medications.

### 7.4.1 Physical Examination

A brief physical examination will be performed on all subjects at Visit 1 (Screening). Height will be collected.

### 7.4.2 Nasal Examination

The nasal examination will be performed via nasoendoscopy; see [Section 6](#), Visit Schedule Summary, regarding completion of this assessment, including visit time windows. The sites will be provided with a nasal examination worksheet and a polyp grading sheet. A summary of the key safety assessments from the nasal examination is provided in [Attachment 3](#). Findings from the nasal examination worksheet that are deemed to be clinically significant by the Investigator will be recorded on the AE CRF beginning at Visit 1 (Screening).

### 7.4.3 Ocular examinations

An ocular examination must promptly be performed if a subject experiences any unexplained worsening in vision during the study (e.g. difficulty reading or seeing traffic signs from a

distance). The examiner must be a health care provider with expertise in examination and diagnosis of conditions of the eye. Reports will be forwarded to the investigator.

#### 7.4.4 Vital Signs and Weight

Vital signs include systolic and diastolic blood pressure measurements and pulse rate. Before vital signs are measured, the subject should be at rest for at least 5 minutes. Weight will be measured at each visit.

#### 7.4.5 Laboratory Variables

Blood and urine samples will be collected at Visit 1 (Screening) for evaluation of laboratory variables shown in [Table 5](#). The total amount of blood to be taken from each subject for these study-specific measurements is approximately 7 mL.

**Table 5: Laboratory Measurements**

Hematology	Serum chemistry
– hemoglobin concentration	• sodium
– red blood cell count	• potassium
– mean corpuscular volume (MCV)	• calcium
– white blood cells (total and differential)	• chloride
– platelet count	• urea
– hematocrit	• creatinine
	• total bilirubin
	• alkaline phosphatase
	• alanine transferase (ALT)
	• aspartate transferase (AST)
	• gamma-glutamyltransferase (GGT)
	• albumin
	• total protein
	• glucose
Urinalysis (dipstick)	Urine Drug Screen
• pH	• cocaine
• glucose	• phencyclidine
• protein	• amphetamines class
• ketone bodies	• benzodiazepines class
• indicators of red and white blood cells	• barbiturates class
	• opiates class
	• propoxyphene
	• methaqualone
	• methadone
• Women of child-bearing potential only: A urine pregnancy test will be performed at each visit, not including Subject Contacts. Subjects continuing treatment past Week 24/Visit 6 will need an additional pregnancy test completed upon returning to site.	

At Visit 6/Week 24/ET, a blood sample will be obtained for SARs COV-2 serology testing.

Blood samples and urine drug screens will be analyzed at a central laboratory facility. Urine samples will be analyzed by dipstick and a microscopic analysis will be performed if the results of dipstick indicate abnormalities to be further investigated. All laboratory reports must be reviewed, signed, and dated by the investigator. A legible copy of all reports must be filed with the subject's source documentation.

If any laboratory tests are performed as part of a subject's standard of care after Visit 1 (Screening) and before Visit 2, Day 1 (Baseline), and a change from the Visit 1 (Screening) laboratory test result is considered by the investigator to be clinically significant, the investigator should reassess the subject's eligibility. If any laboratory tests are performed as part of a subject's standard of care after the subject is randomized, and a change from the Visit 1 (Screening) laboratory test result is considered by the investigator to be clinically significant, it should be considered an AE if it meets the definition provided in [Section 8.1](#). Significant abnormal values occurring during the study will be followed until repeat test results return to normal, stabilize, or are no longer clinically significant.

## 8 SAFETY MONITORING AND REPORTING

### 8.1 Adverse Events

An AE is any untoward medical occurrence associated with the use of an investigational product in humans, whether or not considered related to the investigational product. This includes any occurrence that was new in onset or aggravated in severity or frequency from the baseline condition.

In this study, symptoms of CRS are collected as part of the primary and secondary endpoints. Changes or worsening of symptoms of CRS should not be reported as AEs. All events that meet the definition of a SAE will be reported as SAEs, regardless of whether they are protocol-specific assessments.

Abnormal results of diagnostic procedures, including laboratory test abnormalities, or from the nasal examination are considered AEs if they result in:

- discontinuation from the study treatment or discontinuation from the study
- require treatment or any other therapeutic intervention
- require further diagnostic evaluation which confirms a clinical significant abnormality (excluding a repetition of the same procedure that rules out an abnormality)
- are associated with clinical signs or symptoms that would have a significant clinical impact, as determined by the investigator

Subjects are encouraged to report AEs spontaneously or in response to general, non-directed questioning. All non-serious AEs are to be followed until the subject completes the study or is lost to follow-up.

Timely, accurate, and complete reporting and analysis of safety information from clinical studies is crucial for the protection of subjects, is the responsibility of the investigators and the Sponsor, and is mandated by regulatory agencies worldwide.

Each AE is to be documented on the CRF with reference to intensity, date of occurrence, duration, frequency, treatment, action taken regarding study drug, and outcome. Furthermore, each AE is to be classified as being serious or non-serious. Additionally, the investigator has to assess whether the AE is drug related (adverse drug reaction) or not. Changes of AEs and dates of ending have to be documented on the CRF.

Surgical procedures, planned before enrollment of the subject in the study, are not considered AEs if the condition(s) was (were) known before study inclusion. In the latter case, the medical condition should be reported in the subject's medical history.

For the purposes of this study, the period of observation for collection of AEs extends from the time the subject gives informed consent until completion of the end-of-study visit or an early termination visit. SAEs will be reported through 30 days after the last dose of study drug administration.

The maximum severity (intensity) of the AE will be categorized by the investigator as shown in [Table 6](#).

**Table 6: Adverse Event Severity**

Code	Descriptor	Definition
1	Mild	The subject is aware of the symptom, but easily tolerates it
2	Moderate	The subject has discomfort enough to cause interference with usual activity.
3	Severe	The subject is incapacitated to work or perform the usual activities

## 8.2 Adverse Reactions

An AE is considered related to study drug (adverse reaction) if there is evidence to suggest a causal relationship between the treatment and the AE.

## 8.3 Suspected Adverse Reactions

“Suspected adverse reactions” means any AE for which there is a reasonable possibility that the drug caused the AE. “Reasonable possibility” means there is evidence to suggest a causal relationship between the drug and the AE. A “suspected adverse reaction” implies a lesser degree of certainty about causality than “adverse reaction” which means any AE caused by a drug.

An AE is considered to be a suspected adverse reaction if:

- The AE is a single occurrence of an uncommon AE that is known to be strongly associated with drug exposure (eg, angioedema, hepatic injury, Stevens-Johnson Syndrome).
- The AE occurs 1 or more times and is not commonly associated with drug exposure, but is otherwise uncommon in the population exposed to the drug (eg, tendon rupture).
- The AE is part of an aggregate analysis of specific AEs observed in a clinical trial (such as known consequences of the underlying disease or condition under investigation or other events that commonly occur in the study population independent of drug therapy) that indicates those AEs occur more frequently in the drug treatment group than in a concurrent or historical control group.

Suspected adverse reactions are the subset of all AEs for which there is a reasonable possibility that the drug caused the event. Inherent in this definition and in the requirement to report them, is the need for the Sponsor to evaluate the available evidence and make a judgment about the likelihood that the drug actually caused the AE.

## 8.4 Unexpected Adverse Reactions or Adverse Events

An AE or suspected adverse reaction is considered “unexpected” if it is not listed in the IB or is not listed at the specificity or severity that has been observed. “Unexpected,” as used in this definition, also refers to AEs or suspected adverse reactions that are mentioned in the IB as occurring with a class of drugs or as anticipated from the pharmacological properties of the drug, but are not specifically mentioned as occurring with the particular drug under investigation.

The suspected adverse reactions listed in the IB (ie, “expected”) are those observed with the investigational drug and for which a causal relationship between the event and the drug is suspected or confirmed. Thus, AEs that would be anticipated to occur as part of the disease process are considered *unexpected* for the purposes of reporting because they would not be listed

in the IB. Additionally, AEs that are listed in the IB as occurring with the same class of drugs, or as anticipated from the pharmacological properties of the drug, even though they have not been observed with the drug under investigation, will be considered *unexpected* until they have been observed with the drug under investigation.

## **8.5 Serious Adverse Events**

An AE or suspected adverse reaction is considered “serious” if at any dosage, in the view of either the investigator or Sponsor, it meets one or more of the following criteria:

- is fatal
- is life-threatening
- results in inpatient hospitalization or prolongation of existing hospitalization
- results in a persistent or significant incapacity or substantial disruption of the ability to conduct normal life functions
- is a congenital anomaly/birth defect

Other important medical events that may not be immediately life-threatening or result in death or hospitalization, based upon appropriate medical judgment, are considered SAEs if they are thought to jeopardize the subject and/or require medical or surgical intervention to prevent one of the outcomes defining an SAE. Since SAEs are critically important for the identification of significant safety problems, it is important to take into account both the investigator’s and the Sponsor’s assessment. If either the Sponsor or investigator believes that the event is serious, the event must be considered serious and evaluated by the Sponsor for expedited reporting.

All SAEs must be reported to the Sponsor or their designee within 24 hours after the investigator becomes aware of the event, along with a determination as to whether it is associated with the study drug, device, or procedure.

### **8.5.1 Life-Threatening Adverse Events**

An AE or suspected adverse reaction is considered “life-threatening” if, in the view of either the investigator or Sponsor, its occurrence places the subject at immediate risk of death. It does not include an AE or suspected adverse reaction that, had it occurred in a more severe form, might have caused death. As with the definition of serious, the determination of whether an AE is life-threatening can be based on the opinion of either the investigator or Sponsor. Thus, if either believes that it meets the definition of life-threatening, it must be considered life-threatening for reporting purposes.

### **8.5.2 Serious Adverse Event Reporting**

All SAEs must be reported within 24 hours to:

PPD  
**Safety Email:** [[contact]](mailto:[contact])  
**Safety [contact]

Note: If the contact information above changes during the course of the study, written notification will be provided by the Sponsor or their designee to the investigator, and a protocol amendment will not be required.

It is imperative that PPD be informed within 24 hours after the investigator becomes aware of a SAE so that reporting to the Regulatory Agencies can be met within the required time frame (7 or 15 calendar days).

Because of the need to report to health authorities all SAEs in a timely manner, it is vitally important that an investigator report any AEs that would be considered serious within 24 hours, even if the investigator does not consider the AE to be clinically significant or drug-related.

Should the investigator become aware of an SAE (regardless of relationship to study drug) that occurs within 30 days after stopping the study drug, the SAE must be reported in accordance with the procedures specified in this protocol. There is no time limit on the collection of SAEs that are considered related to study drug.

All SAEs that are not resolved by the end of the study, or that were not resolved upon discontinuation of the subject's participation in the study, are to be followed until either: the AE resolves, the AE stabilizes, the AE returns to baseline values (if a baseline value is available), or it is shown that the AE is not attributable to the study drug or study conduct.

Medical and scientific judgment is to be exercised in deciding whether expedited reporting is appropriate in other situations, such as for important medical events that were not immediately life-threatening or did not result in death or hospitalization but are jeopardizing the subject or require intervention to prevent one of the outcomes listed above.

## **8.6 Non-Serious Adverse Event Reporting**

Non-SAEs will be recorded in the clinical data base in a timely manner to permit review by the Sponsor.

## **8.7 Pregnancy**

Following administration of study drug, pregnancy cases in any female subject will be reported if known until the subject completes or withdraws from the study. The pregnancy will be reported immediately by phone and by faxing/emailing a completed Pregnancy Report to the Sponsor or their designee within 24 hours of knowledge of the event. The pregnancy will not be processed as an SAE; however, the investigator will follow the subject until completion of the pregnancy and must assess the outcome in the shortest possible time but not more than 30 days after completion of the pregnancy. The investigator should notify the Sponsor or their designee of the pregnancy outcome by submitting a follow-up Pregnancy Report. If the outcome of the pregnancy meets the criteria for immediate classification of an SAE (eg, spontaneous or therapeutic abortion [any congenital anomaly detected in an aborted fetus is to be documented], stillbirth, neonatal death, or congenital anomaly), the investigator will report the event by phone and by faxing/emailing a completed SAE form to the Sponsor or designee within 24 hours of knowledge of the event. Pregnancy in the partners of research subjects does not need to be reported.

## **9 STATISTICAL ANALYSIS**

A detailed Statistical Analysis Plan (SAP) will be prepared after the protocol is approved. This document will provide further details regarding the definition of analysis variables and analysis methodology to address all study objectives. Statistical analysis principles to address all study objectives are provided below.

### **9.1 Sample Size Determination**

Sample size assumptions were generated based on previous Phase 3 studies of OPN-375 in subjects with nasal polyposis and data from a study evaluating the change in maxillary and ethmoid opacification in CRS patients treated with an intramuscular dose of triamcinolone ([Pallanch 2013](#)). Based on the results for changes from baseline in morning symptoms among subjects with nasal polyps in the previous studies conducted with OPN-375, a sample of 111 subjects per group (333 total subjects) is sufficient to detect a 0.8 scale difference in morning symptoms score between treatments (OPN-375 vs placebo) using a 2-sided test at the 5% significance level with 88% power, and assuming a standard deviation (SD) of 1.9. This sample size is also adequate to detect an 11.3% difference between treatments in average percent opacification using a 2-sided test at the 5% significance level with 88% power, and assuming a SD of 27 percent. Approximately 333 subjects (111 subjects per group) will be randomized to have at least 120 subjects without nasal polyps be included. The sample size was estimated for the co-primary efficacy endpoints using Power Analysis and Sample Size Software (PASS 15) ([NCSS, 2017](#)).

### **9.2 Analysis Sets**

#### **9.2.1 Intent-to-treat Analysis Set**

The intent-to-treat (ITT) analysis set will include all subjects who are randomized regardless of whether they received double-blind treatment.

#### **9.2.2 Safety Analysis Set**

The safety analysis set will include all randomized subjects who receive at least one dose of randomized study drug. The treatment group assignment in this population will be defined by the treatment actually received. The safety population will be used for the analysis of safety.

#### **9.2.3 Full Analysis Set (FAS)**

The FAS will include all subjects in the ITT set who receive at least one dose of randomized study drug during the double-blinded treatment phase and have at least one baseline efficacy measure for APOV endpoint, and also have a baseline value and at least one post-baseline value (7-day average AM instantaneous CSNS score) on or before Week 4 (i.e., Week 2 and/or Week 4) for the CSNS endpoint. Subjects will be included in the treatment group to which they were randomized.

The FAS population will be the primary study population for all efficacy analyses in this study.

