#### **9.2.4 Per-Protocol Analysis Set (PPS)**

The PPS analysis set excludes subjects from the FAS population due to major protocol deviations with potential to substantively affect the results of the primary efficacy analysis. The PPS population will be used for a sensitivity analysis for primary and key secondary efficacy endpoints.

Determination of the major protocol deviations will be made prior to unblinding of the database and documented in a separate report.

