5.5 Full Analysis Set (FAS)

The FAS will include all subjects in the ITT set who receive at least one dose of randomized study treatment during the double-blinded treatment phase and have a baseline efficacy measurement for APOV endpoint, and also have a baseline value and at least one post-baseline value (7-day average AM instantaneous CSNS score) on or before Week 4 (i.e., Week 2 and/or Week 4) for the CSNS endpoint. Subjects will be included in the treatment group to which they were randomized.

The FAS population will be the primary study population for all efficacy analyses in this study.

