6.1 Subject Disposition

The number of subjects in the Enrolled Set, Single-Blind Analysis Set, ITT Analysis Set, Safety Analysis Set, FAS, PPS will be summarized using descriptive statistics by treatment group and overall.

Subjects who completed the study, and subjects who discontinued the study prior to week 24, will be summarized by treatment group and overall, and reasons for study discontinuation will be summarized.

The denominator for calculating percentages in the Subject Disposition displays will be the ITT Analysis Set.

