For the treatment policy estimand, (reference Section 7.1.3, criteria 3, c), missing data due to study discontinuation will be imputed with a pattern mixture model (PMM) multiple imputation (MI) using the Jump-to-Control (J2C) method. The PMM assumes that the missing data at Week 24/ET on the control arm (placebo) is MAR, and the missing data on the active treatment arms have the profile of the control arm at Week 24/ET.

Multiple imputation using a PMM with J2C method will be conducted using the sequential modeling method as described in (O'Kelly & Ratitch, 2014). Further detail on the MI implementation, and statistical analysis and inference is provided in Section 10.

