7.2.3 Observed Cases Analysis

A sensitivity analysis will be performed for both co-primary endpoints based on the FAS, observed cases population. For each co-primary endpoint, the observed cases population is defined to include all subjects who have an observed value for that endpoint, irrespective of an intercurrent event, and the observed value is used in the analysis. For both co-primary endpoints, the estimator and estimation methods are the same as described in Section 7.1.5, with the exception that in the observed cases population there are no missing data; consequently, no imputation is required.

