9.3 Efficacy Endpoint Variable Definitions

9.3.1 Daily Nasal Symptoms Diary Assessments

Electronic diaries will be used by subjects during the single-blind placebo run-in period and during the first 12-weeks of the 24-week double-blind treatment phase in this study to capture daily nasal symptoms (i.e., symptom scores for nasal congestion, nasal discharge [anterior and/or posterior], facial pain or pressure sensation, and sense of smell) and the use of approved rescue medication after the Week 4 visit through Week 12 of the double-blind period. Subjects will be instructed to complete the electronic diary twice daily immediately before dosing (AM and PM).

Each morning and evening subjects will record their nasal symptom severity scores using the nasal symptoms scoring scale (Table 9.3) to evaluate their symptoms both immediately preceding the time of scoring (instantaneous), and based on reflection of symptoms over the past 12 hours, with regard to nasal congestion, nasal discharge (anterior and/or posterior), facial pain or pressure sensation, and sense of smell.

AM and PM assessment scores, and instantaneous and reflective scores, are all considered to be separate and distinct measures of nasal symptoms and will be analyzed separately.

Composite Score of Nasal Symptoms (CSNS): The CSNS is defined as the sum of the nasal congestion, nasal discharge and facial pain/pressure for each type of assessment (instantaneous or reflective) at each time point (AM or PM), resulting in four CSNS per day.

Table 9.3: Nasal Symptoms Scoring Scale

Score	Description
0	None
1	Mild – symptoms clearly present, but minimal awareness, and easily tolerated
2	Moderate – definite awareness of symptoms that is bothersome but tolerable
3	Severe – symptoms that are hard to tolerate, cause interference with activities or daily living

Note: Sense of smell, scored as 0=normal, 1=slightly impaired, 2=moderately impaired, 3=absent.

For statistical analyses, the daily AM and PM, instantaneous and reflective, individual nasal symptoms scores, and the CSNS will be averaged weekly, defined as the average of the daily scores for the 7 study days prior to the nominal day associated with each 7-day week; for example, for Week 2, Day 14 is the nominal day and the 7-day average is calculated based on study days 7 to 13.

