Table 9.1 displays the efficacy windows defined for the 7-day average Daily Nasal Symptoms diary and CSNS for each study week from baseline (Visit 2) through Week 12 (Visit 5).

The 7-day average diary score will be derived for each nasal symptom (range 0-3) and CSNS (range 0-9) by time point (AM or PM) and measure (instantaneous or reflective). Thus, there are sixteen 7-day average scores representing the individual nasal symptoms scores: 2 (AM, PM) * 2 (instantaneous, reflective) * 4 nasal symptoms (congestion, discharge, facial pressure, sense of smell), and there are four 7-day average CSNS scores: 2 (AM, PM) * 2 (instantaneous, reflective).

The 7-day average AM, instantaneous CSNS score is the primary efficacy variable in this study.

Missing Diary Data

On any given study day, for time (AM, PM), or measure (instantaneous, reflective), if any of the 3 nasal symptom scores is missing then the CSNS score will be missing for that study day, time, and measure. For both individual symptoms and the CSNS, the average 7-day value will be missing only if there are missing values for all 7 days. For the first week (Study Days 2-6, Table 9.1), the average 5-day value will be missing only if there are missing values for all 5 days.

Intercurrent Events (IE)

If an intercurrent event occurs, under the composite strategy per the primary estimand, a worst score of '3' will be assigned to each of the daily nasal symptoms scores recorded on the day of the IE and for the remaining days in the week in which the IE occurs; that is, the 7-day average score will include actual scores for days up to the IE and then a worst score for diary days recorded on or after the day of the IE. Since CSNS is a composite score as defined above, a worst score of '9' is assigned. Subsequent 7-day average scores will be assigned a worst score for the remainder of the CSNS study period.

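### The single FAS makes a post-baseline CSNS average a condition for the APOV analysis, so a few treated subjects are excluded whom the plan's own estimands would impute or score

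*Protocol*

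**What the plan says.** Protocol 9.2.3 and SAP 5.5 build one full analysis set (FAS) from randomised subjects with at least one double-blind dose and a baseline APOV. For CSNS they add "and also have a baseline value and at least one post-baseline value (7-day average AM instantaneous CSNS score) on or before Week 4", which they specify as Week 2 and/or Week 4. The condition governs membership of the whole set, and the set's scope is general: "The FAS population will be the primary study population for all efficacy analyses in this study".

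SAP 9.3.1 fixes what the diary condition requires. On timing, "for Week 2, Day 14 is the nominal day and the 7-day average is calculated based on study days 7 to 13"; Table 9.1 puts the Week 4 window at Days 21-27. On completeness, "the average 7-day value will be missing only if there are missing values for all 7 days". A day's CSNS is itself missing if any of its three component scores is missing.

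For APOV, criterion 3c of the primary estimand (Protocol 9.3.3, SAP 7.1.3) imputes data missing after study discontinuation. Protocol 9.3.4 and SAP 7.1.5 do this by jump-to-control (J2C), under which "the missing data on the active treatment arms have the profile of the control arm at Week 24/ET". The supplementary estimand (Protocol 9.3.5, SAP 7.2.1) gives treatment discontinuation a poor score.

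The other analysis sets stay inside the FAS or are not used for efficacy:
- Per-protocol set: "The PPS analysis set excludes subjects from the FAS population due to major protocol deviations".
- Observed cases: "A sensitivity analysis will be performed for both co-primary endpoints based on the FAS, observed cases population".
- ITT set: "The denominator for calculating percentages in the Subject Disposition displays will be the ITT Analysis Set". No efficacy analysis on the ITT set is specified.

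**The concern.** The condition suits CSNS. In a likelihood-based repeated-measures model, a subject with no post-baseline value contributes no outcome information, so nothing is lost there. For APOV, and for other endpoints that do not come from the diary, it is a post-randomisation exclusion based on a different endpoint, and neither document gives a reason for it.

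It also removes subjects for whom the plan already has a rule. Someone who leaves in the first week without a follow-up scan is the case that criterion 3c and J2C are written for, but those rules cannot reach a subject outside the FAS. Observed data can be discarded as well. Protocol 4.3 encourages subjects who stop treatment to stay in the study, and Protocol 6.5 asks early withdrawals back for a CT. A subject may therefore have a Week 24/ET scan and still be left out for lack of diary entries.

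At stake is a small optimistic shift in one co-primary estimate, and a gap between the estimand and the set on which it is estimated.

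**Working it through.** **1. The plan's own figure.** Inputs from Protocol 9.1 and SAP 4.2: 111 per group; two-sided 5%; CSNS difference 0.8, SD 1.9; APOV difference 11.3 points, SD 27. Normal approximation: power = Φ(difference / (SD × √(2/n)) − 1.96).

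- CSNS: 0.8 / (1.9 × √(2/111)) = 3.137; Φ(1.177) = 88.0%.
- APOV: 11.3 / (27 × √(2/111)) = 3.118; Φ(1.158) = 87.7%.

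Both agree with the stated 88%. With the noncentral t distribution they are 87.8% and 87.4%. No dropout allowance is stated.

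**2. Who is excluded.** One day with all three morning instantaneous scores, in Days 7-13 or 21-27, is enough to enter. Entries only in Days 2-6 or 14-20 do not count, because the condition names Weeks 2 and 4. A subject who drops out later, after one complete entry in the Week 2 window, stays in the FAS and receives J2C for APOV. The excluded group is therefore mainly subjects who stop the diary before Day 7, plus any who stay in the study but leave both windows empty.

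**3. Whether any analysis restores them.** The per-protocol and observed-cases sets are drawn from the FAS. The tipping-point analysis (SAP 7.2.4) is a sensitivity analysis of the primary estimand, so it stays within the FAS. The intercurrent-event disposition summary (SAP 6.1.1) also uses the FAS. None restores them.

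**4. Size of the shift in APOV.** Let f be the share of active subjects who are excluded, have no follow-up scan, and would otherwise be imputed by J2C. Take 11.3 as the difference among the rest. An imputed active subject takes the control profile and contributes a difference of 0:

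- J2C difference = (1 − f) × 11.3 + f × 0
- Overstatement from exclusion = 11.3 × f

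This needs no imbalance between arms. Placebo subjects are imputed under missing-at-random, so on that assumption leaving them out does not shift the placebo mean. For excluded subjects who do have a scan, the effect depends on the observed value and cannot be derived from the documents.

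The values of f are assumptions. Noncentral-t power uses the same f in both arms: the FAS rule keeps 11.3 with n = 111 × (1 − f), and J2C keeps n = 111 with the diluted difference. SD is 27 throughout.

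| f | Subjects per arm | Overstatement (points) | J2C difference | Power, FAS rule | Power, J2C |
|---|---|---|---|---|---|
| 1% | 1.1 | 0.11 | 11.19 | 87.0% | 86.7% |
| 2% | 2.2 | 0.23 | 11.07 | 86.7% | 86.0% |
| 5% | 5.6 | 0.57 | 10.74 | 85.7% | 83.9% |

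**The case against.** The strongest reply is that the group is very small. One complete entry in either window is enough, the diary is electronic, and SAP 7.2.4 expects too few discontinuations before Week 4 to justify a CSNS tipping-point analysis. The group excluded here is narrower still. Even at an assumed 5%, the shift is 0.57 / 27 = 0.02 SD. This stands as an argument about size. It does not explain why a CT endpoint needs a diary condition, and the SAP's remarks on early discontinuation (7.1.5 and 7.2.4) concern CSNS.

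Three stronger readings are tempting, and the documents do not support them.

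- A reader might infer that subjects who need systemic steroids or surgery in the first days are dropped instead of being counted as failures, with the larger effect of a 25-point poor score. SAP 9.3.1 gives later weekly averages the worst score after such an event, so these subjects plausibly have the value that the FAS asks for. Neither document says whether an assigned score counts. That silence is all that can be claimed.
- A reader might infer that early dropouts in general escape imputation. The thresholds in step 2 rule this out.
- A reader might infer that exclusions differ by arm. That is possible but not documented, and the J2C result does not depend on it.

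The exacerbation endpoint is also little affected by subjects who leave before Day 7. The model is offset by log follow-up time, and such a subject adds under a week to a 24-week rate.

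**Conclusion.** The point holds in limited form. The CSNS condition removes from the APOV analysis treated subjects with a baseline APOV and no complete morning entry in either diary window. This is at odds with criterion 3c and J2C in the primary estimand, and with the poor-score rule for treatment discontinuation in the supplementary estimand. No specified analysis brings these subjects back.

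The shift favours active treatment and is probably small: about 0.1 to 0.6 points on 11.3 for an assumed f of 1% to 5%, with 0.3 to 1.8 percentage points of power between the two approaches. It rests on the planning difference, on J2C as specified, and on an f that the documents do not give. The status of subjects with early steroid use or surgery is undetermined. The reason to change the rule is consistency between the analysis set and the estimand; nothing here suggests that the trial's conclusion would turn on it.

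**What to change.** Before unblinding, amend Protocol 9.2.3 and SAP 5.5 as follows.

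1. For APOV and the other endpoints that do not use the diary, define the analysis set as randomised subjects with at least one dose and the relevant baseline value. Omit the post-baseline CSNS condition and apply the existing J2C and composite rules.
2. State that CSNS scores assigned under SAP 9.3.1 count as post-baseline values for FAS entry.
3. Report, by arm and with reasons, the treated subjects excluded from each efficacy set.
4. For the pooled key secondary endpoints, align the set with the plan of Study OPN-FLU-CS-3206, which is not among the documents reviewed.

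The cost is wording, that alignment, a slightly more conservative APOV estimate and slightly lower power. The CSNS model loses nothing.
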